18.3. PRESENTATION OF UNITS

If applicable, parameters will be displayed together with the used unit of measurement. The unit of measurement is enclosed in square brackets ([]). This applies to both tables and listings.

18.4. PRESENTATION OF DATES

Where applicable (e.g., in listings), dates will be displayed in ISO8601 format (example: 2014-09-29T12:16, see CDISC 2013). In case of incomplete dates, the imputed one will be listed and a flag will be added to identify what have been imputed:

- D means that the day is imputed;
- M means that the day and month are imputed;
- Y means that the entire date is imputed.

18.5. HANDLING OF MISSING VALUES

At each time point/visit, all subjects still in the study are reported. Missing values will be taken into account as missing in the analysis. The number of observed values and the number of missing values must sum up to the number of subjects in the study at the respective time point/visit.

18.6. VISIT WINDOWS

The performed visits have an analysis window defined in the CIP. In order to collect all of the information provided in the CRF, the performed visits could be recalculated in real visits with larger analysis window as defined in Table 7.

Table 7 : Visit window

Visit	Targeted study day
1 Month assessment	Day 30 ± 7 days
1 to 3 Months visit	between Day 30 and Day 90
1 Year visit	1 year (Day 365) ± 30 days
2 Years visit	2 years (Day 731) ± 30 days
3 Years visit	3 years (Day 1096) ± 30 days
4 Years visit	4 years (Day 1461) ± 30 days
5 Years visit	5 years (Day 1826) ± 30 days

18.7. CONVERSION OF TIME INTERVALS

If a time interval was calculated in minutes, hours or days and needs to be converted into months or years the following conversion factors will be used:

- 1 month = 30.4375 days
- 1 year = 365.25 days

18.8. MANDATORY TABLES WITHOUT DATA

Recommended tables must be created. If no subject qualifies for the table, the header will be created and the table itself will be replaced by “No subject in this category”.

18.9. STORING OF IMPUTATION DATA

The result of all imputation strategies for final analyses (e.g., incomplete start dates of AE), combination of observations [(e.g., combination of consecutive AEs)] and new derived information (e.g., treatment-emergent flag) must be stored in ADaM data set.

[figure not shown]
18.10. HANDLING OF MISSING DATES

The term missing date refers to a completely missing date or to an incomplete date where parts are not available. If the number of AE with missing date information does not exceed 5% the following imputation strategy is applied.

Missing start and stop date will be imputed conservatively, i.e., missing values will be imputed in such a way that the duration of the AE is considered with the longest possible duration and such that, whenever the AE may potentially start after implantation, the AE will be handled as a TEAE. Further information are reported in Section 18.12 (AE start date) and Figure 3 (AE stop date).

A replacement of missing year for AE start information is not foreseen. If needed, this will be considered on a case-by-case decision which must be documented together with the documentation of ADaM data sets.

Figure 3: Graphical overview about the imputation strategy

I1-I4: imputation steps
C1-C4: checkpoints

18.10.1. Assessment of TEAEs

The assessment whether an AE is a TEAE will be done after replacement of missing date information. As the on-treatment-period is defined without time information the assessment of TEAE will be based on the date part of the AEs only.

18.10.2. List of deaths

Deaths will be identified by SAE defined as “fatal” or “leading to death” (SAE criteria).

18.10.3. Time to onset of AE

Time to onset of AE will be calculated based on date of implant and on the imputed value for AE start date.

18.10.4. Duration of AE

Duration of AE will be calculated based on the imputed values for AE start date and stop date.

If duration of AE could not be calculated due to unknown date information the following assessment to categories will be used:

- If the AE is marked as “ongoing” in the e-CRF the duration will be categorized as “ongoing”
- Otherwise the duration category will be set to “missing”.

18.11. TITLES AND FOOTNOTES

Footnotes should include:

- Analysis cut-off date
- The name and version of the coding system for TFLs presenting coded items.

18.12. DATA DERIVATIONS

Table 8 : Data derivation rules

Derived variable	Derivation algorithm
Consented subject	Yes if filled date of consent No, otherwise.
Enrolled subject	Yes if filled date of consent AND patient is not a failure to implant (termination reason= FAILURE TO MEET RANDOMIZATION CRITERIA) No, otherwise.
ITT subject	Yes if Randomization date not empty No, otherwise.
mITT subject	Yes if ITT and the valve is a study valve (as listed in CRF). In case of "other" values, they have to be checked one by one with PM. No, otherwise.
Adherence to Randomization allocation	Yes if "Was the randomized valve implanted?" at first attempt=Yes No, otherwise.
SAF subject	Yes if Randomization and Implant dates not empty No, otherwise.
PP subject	Yes if 
 - Randomization and Implant dates not empty - Adherent to randomization - no major protocol violation (as reported in CRF field). No, otherwise.

Derived variable	Derivation algorithm
Operating room suite time (min)	Implant, Surgical time: Finish time – Start time
Skin-to-skin time (min)	Implant, Surgical time: Finish time – Start time
Extracorporeal circulation time (min)	Implant, Surgical time: Finish time – Start time
Cross clamp time (min)	Implant, Surgical time: Finish time – Start time
ICU stay (minutes)	Intensive Care Unit: [Date/Time of ICU Discharge] - [Date/Time of ICU Admission] If time of ICU discharge is missing it will be set at 23:59 If time of ICU Admission is missing it will be set at 00:00
ICU stay (days)	ICU stay (minutes) / 1440
Time to SAE	Serious Adverse Event (SAE): SAE start date – Surgery date +1
Early, Late SAE	EARLY if Time to SAE ≤ 30 days LATE if Time to SAE > 30 days

Derived variable	Derivation algorithm
Early safety (at 30 days)	
Serious Adverse Event (SAE):
 
YES if at least one (Time to SAE <=30 days) per CEC:
 
 - All-cause mortality - All stroke disabling and nondisabling - Life-threatening bleeding - Acute kidney injury—Stage 2 or 3 (including renal replacement therapy) - Coronary artery obstruction requiring intervention - Major vascular complication - Valve-related dysfunction requiring repeat procedure (BAV, TAVI, or SAVR): SVD and Aortic regurgitation requiring re-intervention 
NO, otherwise

Clinical efficacy (after 30 days)	
Serious Adverse Event (SAE):
 
YES if at least one (Time to SAE >30 days) per CEC or Echo core lab:
 
 - All-cause mortality - All stroke (disabling and nondisabling) - Requiring hospitalizations for valve-related symptoms or worsening congestive heart failure. - NYHA class III or IV (date of assessment >30 days after valve implant) - Valve-related dysfunction: 
 i. (mean aortic valve gradient ≥ 20 mm Hg, EOA ≤ 0.9–1.1 cm² and/or DVI < 0.35 m/s, AND/OR ii. moderate or severe prosthetic valve regurgitation) 
NO, otherwise

Derived variable	Derivation algorithm
Time-related valve safety	
Serious Adverse Event (SAE):
 
YES if at least one (Time to SAE >30 days) per CEC or echo core lab:
 
 - Structural valve deterioration (both points i. and ii. have to be met): 
 i. Valve-related dysfunction: 
 ▪ mean aortic valve gradient ≥ 20 mm Hg, EOA ≤ 0.9(if BSA<1.6 cm²) or 1.1(if BSA≥ 1.6 cm²) cm² and/or DVI<0.35 m/s, AND/OR ▪ moderate or severe prosthetic valve regurgitation) ii. Requiring repeat procedure (TAVI or SAVR) - Prosthetic valve endocarditis - Prosthetic valve thrombosis - Thrombo-embolic event, non-cerebral , - TIA - STROKE - VARC bleeding (BARC type 5, BARC type 3A, 3B and 3C, BARC type 2), unless clearly unrelated to valve therapy (e.g., trauma) : Device and/or procedure related 
NO, otherwise

MACCE (Yes/No)	
Serious Adverse Event (SAE), Valve re-intervention:
 
YES if at least one per CEC:
 
 - Death - Myocardial infarction - Stroke - Reintervention 
NO, otherwise

Derived variable	Derivation algorithm
MACCE @ 1 year (Yes/No)	
Serious Adverse Event (SAE), Valve re-intervention:
 
YES if at least one per CEC:
 
 - Death (Time to SAE <=365 days) - Myocardial infarction (Time to SAE <=365 days) per CEC - Stroke (Time to SAE <=365 days) per CEC - Reintervention (Time to SAE <=365 days) 
NO, otherwise

MACCE @ n year (Yes/No)	
CEC adjudication of Serious Adverse Event (SAE), Valve re-intervention:
 
YES if at least one per CEC:
 
 - Death (Time to SAE <=n*365.25 days) - Myocardial infarction (Time to SAE <= n*365.25 days) per CEC - Stroke (Time to SAE <= n*365.25 days) per CEC - Reintervention (Time to SAE <= n*365.25 days) 
NO, otherwise

PM implant	
SAE FORM – TREATMENT
 
Yes if:
 
 - Was a pulse generator implanted? = YES - If yes, specify = Pacemaker 
NOTE: PM implant will be classified as intraoperative, early or late according to the date of PM implant (not the AE start date)

Derived variable	Derivation algorithm
Last exposure date	
Study Termination, Serious Adverse Event (SAE):
 
 1. For explant of investigational device: date of explant 2. For dead subjects: date of death 3. For alive and not explanted subjects: 
 - Date of termination - If there is no date of termination, the last available FU date (including discharge) or the last SAE date (occurrence date), whichever occurs later. - If there is no follow-up and no adverse events : date of surgery or date of randomization, whichever occurs later.
Last study date	
Study Termination, Serious Adverse Event (SAE):
 
 1. For dead subjects: date of death 2. For alive subjects: 
 - Date of termination - If there is no date of termination, the last available FU date (including discharge) or the last SAE date (occurrence date), whichever occurs later. 
If there is no follow-up and no adverse events : date of surgery or date of randomization, whichever occurs later.

Study length (days)	
Study termination, Subject Information:
 
Last study date – Enroll Date+1

Extent of exposure (days)	
Last exposure date-surgery date+1

Late patients	
Subjects with more than 30 FU days of exposure

Patient-years	
Cumulative Study length (days)/365.25

Derived variable	Derivation algorithm
Early patient-years	Cumulative Study length (days) up to 30 days/365.25
Late patient-years	Cumulative Study length (days) from 31st day/365.25. Subjects with less than 31 FU days do not contribute to the late patient-years
SAE starting date (missing)	In case of missing SAE starting date, the following rule will be applied: 
 1. If missing day: 1st day of the month 2. If missing day and month: 01-JAN 3. If totally missing: Date of surgery SAE starting date cannot be before the surgery date. In that case, SAE starting date will be set as date of surgery.
Deaths	Death is when there is a SAE: 
 - With outcome='FATAL' OR - Leading to death (SAE criteria) The date of death is retrieved from the SAE form (Date of death).
Leak severity	Leak will be classified in: 
 1. none/trace: if "Is there a Paravalvular Leak?" ("Is there a Central Leak?")='No' or severity=' Trace (<1/4+)' 2. mild: if severity=' Mild (1/4+)' 3. moderate/severe: if severity=' Moderate (2/4+)' or severity=' Severe (>= 3/4+)'

Derived variable	Derivation algorithm
Proportion of patient event-free at one year	For each MACCE component: Numerator: #patients who experienced the specific MACCE component within DAY 365 Denominator: #patients who experienced the specific MACCE component within DAY 365 + # patients without the specific event at DAY 365
Proportion of patient MACCE-free at each year	Numerator: #patients who experienced MACCE within DAY 365 (730, 1095, 1460, 1825) Denominator: #patients who experienced MACCE within DAY 365 (730, 1095, 1460, 1825) + # patients without MACCE at DAY 365 (730, 1095, 1460, 1825)
MPG Gradient class	Aortic Mean Pressure Gradient (MPG) class: 
 • MPG \geq 20mmHG • MPG < 20mmHG
Hospitalization time [days]	Discharge – Hospital Admission +1
Ward time [days]	Hospitalization time – ICU time
EQ-VAS	Use as first source of values the “EQ5D02-Your Health Today” variable. If it’s missing, use the “EQ VAS Score” to replace the missing value.
Aortic Mean Pressure Gradient (MPG) with LVOT adjustment	Aortic Mean Pressure Gradient - LVOT Mean Pressure Gradient
Peak Mean Pressure Gradient (MPG) with LVOT adjustment	Aortic Peak Pressure Gradient - LVOT Peak Pressure Gradient

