12.2. NORMALIZED CONSUMPTION INDEX AND REDUCED NORMALIZED CONSUMPTION INDEX

12.2.1. Definitions

According to the CIP (Appendix 3), the Consumption Index (CI) will be define as the sum of all resources consumed, weighted for the contribution of unit cost of each event to the total cost:

$$CI = \sum_{j=1}^n \alpha_j E_j$$

where E_j is the observed value of event j and α_j is the ratio between unit cost of event j and the total cost. The Normalized Consumption Index will be define as a transformation of CI such that it ranges between 0 and 1. The simplest definition is

$$NCI = \frac{CI}{1 + CI}$$

The contributions of each event on the total cost (α_j) are reported in Table 5 and are calculated using result of 4 European countries (Italy, France, Germany, UK).

Table 5 : Contributions of each event on the total cost

Event (within discharge)	a_j	a*_j
OR time (hours – only first attempt)	0.1114	0.1177
Re-operation up to discharge (yes/no) [valve intervention within discharge]	0.2251	
ICU LOS (days)	0.0798	0.0843
Ward LOS (days)	0.0254	0.0268
Transfusion (units during implant and ICU)	0.0093	
Sepsis (yes/no) [from AE]	0.2544	
Was the subject under renal replacement (RRT) therapy in ICU? (yes/no)	0.0092	

Any Permanent Pacemaker Implant	0.2006	
Stroke (yes/no) [from AE]	0.2182	

Since OR time and hospital cost represent more than 95% of total cost for all countries, a reduced Normalized Consumption Index (rNCI) will be define as the previous index but using only OR time, ICU and ward length of stay ($\alpha * j$).

Descriptive analyses for NCI, rNCI, and their components will be reported overall, by treatment and stratified by country.

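### Missing ICU clock times are filled with the longest stay the dates allow, so a same-day ICU admission can start before the operation; floor it at the recorded OR finish time

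*SAP*

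**What the plan says.** SAP section 18.12 (Table 8) derives ICU stay in minutes as the difference "Date/Time of ICU Discharge] - [Date/Time of ICU Admission" and divides by 1440 for days. Two fill-in rules follow: "If time of ICU discharge is missing it will be set at 23:59" and "If time of ICU Admission is missing it will be set at 00:00". Neither rule refers to the operation. The same table derives operating room suite time from a recorded start and finish time. It derives ward time as "Hospitalization time – ICU time", where hospitalization time is discharge minus admission plus one day.

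SAP section 12.2.1 (Table 5) gives the weights, for NCI and then rNCI:
- "ICU LOS (days) 0.0798 0.0843"
- "Ward LOS (days) 0.0254 0.0268"
- "OR time (hours – only first attempt) 0.1114 0.1177"

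The reduced index is built "using only OR time, ICU and ward length of stay". NCI is CI/(1 + CI).

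SAP section 12.2.2 tests both indexes for superiority and requires both to succeed. If under 5% of index values are missing, it uses complete cases and a Wilcoxon-Mann-Whitney test. Otherwise it uses multiple imputation with ANCOVA, backed by a complete-case sensitivity analysis.

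**The concern.** ICU information is collected with the hospital discharge data (Protocol 8.7.1), so the admission in question is taken to be the postoperative one. If it is dated the day of surgery, midnight at the start of that day precedes the operation. The derived stay then includes hours when the patient was not yet in the ICU, although the OR finish time that rules this out is already recorded.

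ICU days carry about three times the weight of ward days, and ICU stay is one of only three items in rNCI. Superiority in resource consumption is a stated aim in the Protocol introduction.

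The fill-in is also invisible to the safeguards in SAP 12.2.2. Once a clock time has been supplied, the patient has a complete index. He or she does not count towards the 5% trigger and stays in the complete-case analysis. No sensitivity analysis of the filled-in times is planned.

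**Working it through.** **Inputs from SAP Tables 5 and 8.** NCI weights: OR 0.1114 per hour, ICU 0.0798 per day, ward 0.0254 per day. rNCI weights: 0.1177, 0.0843, 0.0268. Ward time = hospitalization time − ICU time.

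**Assumed, because the documents give no figure.** True ICU admission between 12:00 and 18:00 on the day of surgery, true ICU discharge near 11:00, and 1% to 20% of an arm lacking clock times. Illustrative patient: 4 h OR, 2 ICU days, 10 hospital days, so 8 ward days, with no other NCI item.

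**Check of the plan's own weights.** The rNCI weights should be the NCI weights times one common factor, 0.1177/0.1114 = 1.0566. ICU: 0.0798 × 1.0566 = 0.0843. Ward: 0.0254 × 1.0566 = 0.0268. Both match Table 5. The ICU/ward ratio is 0.0798/0.0254 = 3.14.

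**Excess ICU days.** Excess = (true admission clock time − 00:00) + (23:59 − true discharge clock time), counting only the term whose time is missing. The ceiling is 1439/1440 = 0.999 day per missing time, or 1.999 days for both.

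**Net effect per excess ICU day.** Each hour added to ICU time is taken off ward time.
- NCI: 0.0798 − 0.0254 = 0.0544 on CI
- rNCI: 0.0843 − 0.0268 = 0.0575 on the reduced CI
- OR equivalent: 0.0544/0.1114 × 60 = 29 minutes

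**Per affected patient (NCI weights).**

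| Missing | Assumed true time | Excess days | Net CI | OR-minute equivalent |
|---|---|---|---|---|
| Admission | 12:00 | 0.50 | 0.0272 | 15 |
| Admission | 14:00 | 0.583 | 0.0317 | 17 |
| Admission | 18:00 | 0.75 | 0.0408 | 22 |
| Both | 14:00 and 11:00 | 14/24 + 779/1440 = 1.124 | 0.0612 | 33 |

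**On the tested scale (illustrative patient, both times missing).**
- NCI: CI = 4 × 0.1114 + 2 × 0.0798 + 8 × 0.0254 = 0.8084, so NCI = 0.8084/1.8084 = 0.447. After the rule, CI = 0.8696 and NCI = 0.8696/1.8696 = 0.465, a rise of 0.018.
- rNCI: 0.8538/1.8538 = 0.461. After adding 1.124 × 0.0575 = 0.0646, 0.9184/1.9184 = 0.479.

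**Arm mean, both times missing.** Shift = share × 0.0612.
- 1%: 0.0006
- 5%: 0.0031
- 10%: 0.0061
- 20%: 0.0122

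On NCI, using the illustrative rise of 0.018, the range is about 0.0002 (1%) to 0.0036 (20%).

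**The case against.** The case for leaving the rule alone has real weight.

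- It is prespecified and identical in both arms. With equal missingness and equal clock times, the expected difference in mean CI does not move, and added noise tends to work against a superiority claim. This stands.
- The Wilcoxon-Mann-Whitney test limits the pull of single values when under 5% of indexes are missing. This stands for that branch.
- A discharge time of 23:59 is extreme but possible. This stands: only the 00:00 rule with a same-day admission produces an impossible value.
- EDC edit checks and source data verification (Protocol 13.1 and 14) should keep missing times few. They make this likely but do not guarantee it.
- Longest-duration imputation is already the SAP's convention for missing adverse event dates (18.10), where it is called conservative. This carries over poorly, because lengthening stays in a two-arm superiority comparison has no known conservative direction.

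A reader might infer that the rule creates a double count of operating hours. It does not. Hospitalization time counts the whole day of surgery, so for a patient with complete times the OR hours already sit in ward time. The rule moves them from ward weight to ICU weight.

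For the same reason the gross figure, 1.124 × 0.0798 = 0.090, never reaches the index, because the ward offset always applies. Nor is any weight inflated: the weights are fixed, and only the days they multiply change.

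**Conclusion.** The point holds as a derivation defect of modest, unquantified overall effect. A missing admission time on the day of surgery gives an ICU start that precedes the operation, assuming the recorded ICU stay is the postoperative one. For an affected patient the net rise in CI (NCI weights) is 0.027 to 0.041 if admission time alone is missing, and 0.061 if both times are missing, under the assumed clock times. The effect on an arm mean depends on a share of missing times that the documents do not give.

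A reader might go further and conclude that the superiority tests are biased towards one valve. The documents do not support that. Bias needs missingness or clock times that differ by arm, and nothing in the plan shows either. The open design makes a difference possible, no more. Only NCI, rNCI and the ICU and ward stay summaries are affected; the primary MACCE analysis is not. The change is worth making because it removes impossible values from two formally tested secondary indexes, and because the missing-data provisions of section 12.2.2 would not reveal them.

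**What to change.** In SAP Table 8:

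1. When ICU admission is dated the day of surgery and its time is missing, set it to the recorded OR finish time.
2. Never allow ICU admission before OR finish.
3. Report the number of imputed ICU admission and discharge times by arm.
4. Keep 00:00/23:59 as a sensitivity bound.

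Optionally, replace a missing discharge time with the median observed discharge clock time, pooled over arms. This is a secondary choice and is itself a single imputation.

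For an assumed 14:00 admission with only that time missing, the first change takes the excess from 0.583 day to about zero and removes 0.032 net from CI (0.034 from the reduced CI).

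The cost is two changed lines in Table 8 and one extra sensitivity run; OR times are already collected. OR finish is only a lower bound for ICU admission, so the stay may still be overstated by the transfer time.

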8.5.8 TRIAL ENDPOINTS DEFINITION AND ASSESSMENTS

The primary endpoint will be evaluated in a non-inferiority setting, with statistical hypothesis tests formally defined in section 10.

Primary endpoint

The primary endpoint is freedom from MACCE (composite endpoint of all cause death, myocardial infarction, stroke, and valve re-intervention) at one year based on CEC adjudication.

The definitions of each component endpoint are reported in the **Table 4** below, complete definitions can be found in Appendix 4.

Table 4 Definitions of the single endpoint of MACCE

Endpoint	Definition
All cause of death	Total number of deaths regardless of cause (cardiovascular mortality + non cardiovascular mortality)
Myocardial infarction	Myocardial injury as specified in VARC-2 [1]
Stroke	Stroke is defined as an acute episode of focal or global neurological dysfunction caused by the brain, spinal cord, or retinal vascular injury as a result of hemorrhage or infarction. A stroke may be classified as “undetermined” if there is insufficient information to allow the categorization as ischemic or hemorrhagic.
Valve Re-intervention	Any re-intervention, including a transcatheter valve implant, on the implanted aortic valve bioprosthesis after surgical closure of the chest.

Secondary endpoints

1. Surgical time
 - a. Cross clamp time during index procedure
 - b. Cardiopulmonary bypass time during index procedure
2. Normalized Consumption Index and reduced Normalized Consumption Index, including resource consumption items such as (but not limited to):
 - a. Operative room time,
 - b. Duration of ICU/CCU and total hospital stay
 - c. Incidence of specific serious adverse events as defined in Appendix 3
 - d. Blood transfusion(s)
3. Quality of life questionnaire
 - a. At 1 month and 1 year post surgery
4. Intraprocedural and periprocedural serious adverse events regardless of relationship with the device within 72 hours.
5. All valve and procedure relevant serious adverse events as specified in VARC-2 guidelines [1] (Appendix 7)
 - a. Early safety at 30 days
 - b. Clinical efficacy after 30 days
 - c. Time related valve safety: SVD, endocarditis, thrombosis, thromboembolic events (excluding stroke), and bleeding annually up to 5 years
6. Serious device related adverse events up to 5 years
7. Freedom from MACCE at 2, 3, 4 and 5 years of follow up
8. Pacemaker implantation and cause up to 1 year

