17.2 INVESTIGATOR’S RESPONSIBILITIES IN AE REPORTING

- a) The Principal investigator is required to report the following serious adverse events to the Sponsor:
- All MACCE (deaths, MI, Stroke and valve re-intervention) and USADEs throughout the trial duration up to 5 years.
 - All other serious adverse events up to 5 years including: structural valve deterioration, non-structural valve dysfunctions, endocarditis, thromboembolic events, and valve thrombosis.

Table 10 Adverse Events Reporting to the Sponsor

	Subject Visit					
	Point of enrollment	Implant	Discharge	Late Post-op (1-3 Mo.)	1 Year (11-13 Mo.)	Annual Follow-up
All Deaths, USADE, SAE	x	X	X	X	X	X

The following timelines for reporting should be followed (**Table 11**):

- Unanticipated Serious Adverse Device Effects (USADE) should be reported to the Sponsor immediately within 24 hours by notifying the Sponsor Clinical Project Manager and by entering the information in the EDC. These events require urgent investigation by the Sponsor and reporting to regulatory authorities, as applicable.
- Serious adverse events should be reported as soon as possible but no later than 3 calendar days upon awareness. The investigator should enter all available information in the SAE section of the EDC system.
- Device deficiencies should be reported within 3 calendar days of awareness. Deficiencies of the Sorin study device should be reported in the EDC. The investigator must return the device, if possible, to the Sponsor. Deficiencies of the non-Sorin study device should be reported following the commercial reporting procedure for that device.

Table 11 Timelines and Communication Methods for Reporting Serious Adverse Events

Event Classification	Communication Method	Communication Timeline
USADE	Contact Clinical Project Manager Complete AE eCRF page with all available information.	Within 24 hours of awareness
Serious Adverse Event including deaths and SADE Device Deficiencies (including but not limited to failures, malfunctions, and product nonconformities including labeling and packaging issues)	Complete AE eCRF page with all available information.	Within 3 calendar days of first becoming aware of the event or as per local/regional regulations. Reporting of any updated information required through the end of the trial
	Provide all relevant source documentation (unidentified) for reported event	When documentation is available

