13.1.2. Adverse Events Incidences

The incidence of AE is defined as the number of subjects with occurrence of this AE during the period of interest. The incidence rate (CIR for crude incidence rate) of an AE is defined as the number of subjects with occurrence of this AE during the period of interest divided by the total number of subjects n in the respective group (e.g., treatment group).

The incidence, incidence rate, the number of events and the percentage of events (related to the total number of events) will be summarized by AE term over the entire study post-implant period (from Day 1) and during the early and late phases (section 18.12). For the late events, the incidence rate will be calculated on the number of late patients only.

In addition, safety summaries will be done according to the following plan:

- Intraprocedural and periprocedural (within 72 hours) serious adverse events regardless of relationship with the device.

- All valve and procedure relevant (according to CEC adjudication) serious adverse event composite endpoints and their components as specified in VARC-2 guidelines (and reported in section 18.12):
 - Early safety at 30 days
 - Clinical efficacy after 30 days
 - Time related valve safety annually up to 5 years
- Serious device related (according to CEC adjudication) adverse events up to 5 years (from day 1 up to Day 1826)
- Postoperative site-reported unexpected serious adverse device effect (USADE)
- Site-reported relationship to procedure, device, drug/medication, or other Protocol Required Assessment (section 18.12)
- All late serious adverse events will be analyzed according to a constant hazard model: the linearized rates will be calculated as:
 - total number of late events divided by the total time under evaluation after 30 days (late patient-years).
 - number of patients with at least one late event divided by the total time under evaluation after 30 days (late patient-years).
- The incidence, incidence rate, the number of events and the percentage of Pacemaker (PM) implantation according to:
 - time of occurrence (overall, early, late and up to 1 year), and
 - relationship to device and procedure.

In addition, time-to-event methods (section 5.2) will be used to summarize the time to onset of the following events:

- deaths (overall, cardiovascular, and non-cardiovascular),
- explants and
- all main cardiovascular SAEs:
 - Bleeding,
 - SVD,
 - endocarditis,
 - valve thrombosis,
 - thromboembolic events,
 - stokes,

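### The 30-day early-safety derivation narrows valve dysfunction needing a repeat procedure to SVD and aortic regurgitation, so some early repeat procedures go uncounted

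*SAP*

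**What the plan says.** Early safety at 30 days is secondary endpoint 5a (Protocol 8.5.8). SAP 13.1.2 promises "composite endpoints and their components as specified in VARC-2 guidelines (and reported in section 18.12", so Table 8 is the operative rule.

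The early-safety row scores a subject "YES if at least one (Time to SAE <=30 days) per CEC" of the listed items, and as no event otherwise. Its only item on valve re-intervention is "Valve-related dysfunction requiring repeat procedure (BAV, TAVI, or SAVR): SVD and Aortic regurgitation requiring re-intervention".

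Three other places bear on how that item is read:

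- **Event categories.** Protocol 17.2 has investigators report, as separate terms, "structural valve deterioration, non-structural valve dysfunctions, endocarditis, thromboembolic events, and valve thrombosis". SAP 13.1.2 likewise gives SVD, non-structural dysfunction (NSVD), valve thrombosis, central leak and perivalvular leak their own time-to-onset summaries.
- **SVD.** The SAP's only working definition is in the time-related valve safety row of Table 8: "Structural valve deterioration (both points i. and ii. have to be met". Point i is abnormal haemodynamics (the entry begins "mean aortic valve gradient ≥ 20 mm Hg, EOA ≤ 0.9(if BSA<1.6 cm²") and/or moderate or severe regurgitation. Point ii is "Requiring repeat procedure (TAVI or SAVR".
- **Re-intervention in MACCE.** Protocol 8.5.8, Table 4, counts "Any re-intervention, including a transcatheter valve implant, on the implanted aortic valve bioprosthesis after surgical closure of the chest", with no restriction by cause.

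**The concern.** A derivation table is programmed as it stands. Here the component's name and its content differ: the name covers valve-related dysfunction in general, while the content is two diagnoses. Nothing marks the list as illustrative, and every unlisted case defaults to no event.

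Two categories that the documents separate from SVD, NSVD and valve thrombosis, are absent. Thrombosis enters a Table 8 composite only through the time-related row, which starts after day 30. An early repeat procedure for thrombosis that is neither regurgitant nor classed as SVD therefore falls outside both composites.

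The Perceval valve anchors without sutures and the control valve is sutured, so repeat procedures in the first month are of direct interest in this comparison. A 30-day composite should count them by a rule that does not depend on how the mechanism is labelled.

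**Working it through.** The documents state no figure for this component, so there is none to reproduce. The check applies the row to each type of repeat procedure by day 30 under three readings:

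- **A:** the component's name alone, before the colon.
- **B:** the text after the colon, using the adjudicated labels SVD and aortic regurgitation.
- **C:** as B, but with the SVD definition from the time-related row carried into the early row.

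| Repeat procedure by day 30 for | A | B | C |
|---|---|---|---|
| Dysfunction adjudicated as SVD | counted | counted | counted |
| Aortic regurgitation | counted | counted | counted |
| Obstruction meeting the gradient, EOA or DVI criteria, treated by TAVI or SAVR | counted | not counted | counted |
| The same obstruction, treated by BAV | counted | not counted | not counted |
| NSVD (including displacement) or thrombosis causing dysfunction, with neither regurgitation nor those haemodynamic criteria | counted | not counted | not counted |

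The rows lead to the following:

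1. **Last row.** B and C agree with each other and disagree with the component's own name. This gap does not depend on which SVD definition is used. The subject is scored as having no event unless another listed component occurs: death, stroke, life-threatening bleeding, stage 2 or 3 kidney injury, coronary obstruction requiring intervention, or a major vascular complication.
2. **Obstruction rows.** The result turns on a definition the early row does not cite. Even when it is imported, BAV drops out: the SVD definition requires TAVI or SAVR, although the early row names BAV.
3. **Regurgitation row.** The row does not say whether aortic regurgitation includes paravalvular leak. Protocol 8.5.8 lists AI and PVL as separate echo parameters, while SAP 11.2.2 treats paravalvular and central leaks together as regurgitations.
4. **Against MACCE.** Any re-intervention after chest closure and within 365 days is a MACCE event in Table 8. The same day-10 re-intervention can be a primary-endpoint event and leave early safety scored as no event.

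**Size.** No 30-day re-intervention rate by cause is given. The nearest figures are one-year reoperation rates from single-arm Perceval studies (Protocol 6.2): 1.9% in CAVALIER (valve-related), and 100 − 94.7 = 5.3% in the pivotal trial. Applied to 617 subjects, the arm size at the maximum sample:

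- 0.019 × 617 = 11.7
- 0.053 × 617 = 32.7

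If those rates carried over, they would give about 12 to 33 subjects over a full year and for every cause those rates include. The affected group (by day 30, non-regurgitant, outside the SVD criteria) would be a smaller subset. Its size cannot be derived.

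**The case against.** The strongest reply is that the gap is small and these events are not lost.

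- **SVD as the SAP defines it is broad.** It rests on haemodynamics or regurgitation plus a repeat procedure, and so does not depend on mechanism. This stands in part. A reader might infer that early re-intervention for obstruction is excluded outright, or that only regurgitation can trigger the component. Neither is established. What remains is that the early row does not cite the definition, and that the definition omits BAV.
- **SVD is not confined to day 31 onward.** A reader might take it so, because the definition sits in a row for events after day 30. That limit is the window of the time-related composite, not part of the SVD definition, and the early row itself uses SVD by day 30.
- **Anchoring failure often shows as a leak.** The SAP's use of regurgitation in 11.2.2 makes it plausible that paravalvular leak already counts, and coronary obstruction requiring intervention is a separate component. This narrows the gap without closing it.
- **The events appear elsewhere.** SAP 13.1.2 summarises events by term in the early and late phases and gives NSVD, thrombosis, leaks and explants their own time-to-event summaries. SAP 11 analyses each MACCE component. This stands: the trial will see these events. It does not correct the composite reported as endpoint 5a.
- **VARC-2, the Appendix 4 definitions and the CEC Charter are not in the documents reviewed.** Whether the two named diagnoses follow the cited source cannot be checked. This limits the finding to a mismatch within the SAP.

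**Conclusion.** The derivation rule is narrower than the component it implements. A repeat procedure by day 30 for non-structural dysfunction or valve thrombosis, without regurgitation and without meeting the SVD criteria, is scored as no event unless another component occurs. Obstruction and paravalvular leak are left to interpretation.

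The consequence is limited. Endpoint 5a is secondary, SAP 13 summarises safety data descriptively, and the primary endpoint counts every re-intervention after chest closure.

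Two stronger conclusions are tempting and unsupported. The first is that the rule favours Perceval. The same rule applies to both arms, and no document gives non-regurgitant early failure by arm, so the direction is unknown. The second is a patient count. Assuming that 30% to 60% of reoperations fall by day 30 and 25% to 50% of those are non-regurgitant gives 0.019 × 0.30 × 0.25 = 0.14% to 0.053 × 0.60 × 0.50 = 1.59%, or about 1 to 10 of 617. Both fractions are assumptions with no source in the documents. Protocol 6.2 also reports no migration or dislodgement in the pivotal trial and no migration or thrombosis in CAVALIER. The number should be treated as unknown and possibly very small.

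The conclusion assumes that the list after the colon will be programmed as exhaustive, which is how the row reads.

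**What to change.** In SAP 18.12, Table 8, early-safety row, delete the restriction after the colon so that the component reads in substance:

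> Any CEC-adjudicated repeat procedure (BAV, TAVI or SAVR) by day 30 for valve-related dysfunction of any mechanism, including non-structural dysfunction, obstruction, and paravalvular or central regurgitation.

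Check this against the VARC-2 definition that the SAP cites. If the two differ, the SAP should say where and why. Tabulate the mechanism of each counted procedure by arm, so that the composite can be read alongside the separate SVD, NSVD, leak and thrombosis summaries. Make the change before database lock and record it in the SAP change history.

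The cost is one line of text and one small table. No new data are needed, because under Protocol 11.4 the CEC already adjudicates valve re-intervention and explantation whatever the cause. The downside is that the early-safety event rate may be slightly higher.
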